Each of these components have multiple procedures to safeguard the wellbeing of study subjects and to maintain the scientific integrity of the project while achieving the study's specific aims. Key components of the data and safety monitoring plan include weekly meetings of core members of the research team (at minimum, the Principal Investigators, Project Director and Research Assistants) and monthly meetings of the extended research team including [name], [name], [name], [name], [name], [name], [name], [name], site prevention nurses and research coordinators.

Meetings of Core Members of the Research Team:

The PIs will run monthly conference calls with the entire study team which will include core protocol team along with study coordinators, prevention nurses, and other representatives from each of the 3 study sites. The agenda for these meetings will include tracking of subject recruitment, enrollment, and retention; data collection and entry; and documentation and review of any subject concerns or adverse effects. These meetings will help ensure that the project timeline is being met.

Regulatory Issues

Adverse Events Protocols:

An adverse event is defined as any reaction, side effect, diagnosis or untoward event that either a) occurs during the course of the clinical trial and was not present at baseline; or b) was

present at baseline and appears to worsen during the study. All AE's will be reported to one of the study PIs. All subjects will be aware of their rights prior to participation and will be encouraged to report any incidents or adverse effects to the investigators and the Case Western Reserve University Institutional Review Board (IRB). Contact information for the investigators and the IRB will be provided in all the consent materials. During assessments the research staff will inquire about AEs and complete an AE form for each subject. In the event that the participant is experiencing a worsening of symptoms, the Research Assistant will, with participant's permission, inform the clinic director. The study PIs, and research staff will together determine if the AE places the participant at risk if study treatment is continued.

All adverse events, with the exception of clinically insignificant events and minor common illnesses and injuries (e.g., cold/flu, scrapes, upset stomach, low-grade headaches) will be documented on an AE Log. Should any study subjects express concerns about the study and/or their participation in the study or express distress as a result of their participation, the witnessing research team member will document this in the AE Log. AEs will be reported to the study PIs and the study research staff to determine whether and what actions might be appropriate. Any AEs determined to be serious and/or study-related will require the completion of an AE form to be entered into the project database.

During research staff training, procedures for AE identification, collection and reporting will be reviewed in detail. Study staff will be trained to provide crisis intervention and referral as is standard operating procedure within each clinic for such situations, should they become dangerous or life-threatening (i.e. suicidal ideation or attempts).

AEs will be managed in conjunction with clinic medical staff, with permission from the participant. All subjects will be ongoing patients at a study site clinic and thus subjects can be monitored and have access to medical staff throughout the study period.

Data and Safety Monitoring Board

According to guidelines established by the NIH for clinical trials, the investigators will establish a Data and Safety Monitoring board (DSMB) composed of independent research scientists not otherwise connected with the study. This committee (which is independent of the study investigators) will be set up to monitor the study results for evidence of adverse or beneficial treatment effects throughout the study period. The Monitoring Committee will remain "blinded" to outcome characteristics of the study for as long as possible. While the committee may have access to information that is deemed necessary to make an appropriate determination, highly sensitive information in relation to the outcome of the study will be requested on a "need to know" basis as it may arise during the course of the committee's deliberations. The committee's concerns will be directed to patient accrual rates, appropriate follow-up, compliance, data acquisition, undue complications, and whether the study as it is currently being conducted will be able to answer the proposed hypotheses. Additional responsibilities will include monitoring the integrity of data collection, reviewing training and compliance with all components of the interventions and monitoring for adverse events. The membership and frequency of meeting are at the discretion of the funding institute but will consist of 3-5 members with appropriate expertise, for example in biostatistics, cardiovascular disease, behavioral interventions, HIV research, and clinical trials. It is expected that this committee will meet once per year in person and once via conference call and will report to the funding institute on scientific and administrative issues. We do not anticipate any real harm to patients, but adverse

events will be monitored. Adverse event forms will be used to report all unanticipated events. The following information will be included in the report: date of event, attribution to intervention, and outcome of adverse events. Death will be reported within 24 hours. Unanticipated adverse events will be reported within 7 days. Reports will be submitted electronically to the CWRU IRB and NIH. A written follow-up will be submitted within 30 calendar days. All adverse events (serious or not, related or unrelated, anticipated or unanticipated) will be reported in the annual report to the CWRU IRB and NIH.

The DSMB members and contact information is shown in the following table (members appointed Jan 2019):

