PLHIV (n=110; n=35 per site)	
1. Age \geq18 years2. Confirmed HIV+ diagnosis3. Undetectable HIV viral load: defined as the most recent HIV viral load <200 copies/mL, checked within the past year (assessed via chart abstraction), and4. Hypertension without hyperlipidemia (both defined in parent trial), or5. Hypertension and hyperlipidemia but unable/unwilling to enroll in the parent trial.6. Previously enrolled in the parent trial and interested in improving hypertension management through a virtual format.	Same as parent trial criteria outlined in aim 2.

Withdrawal:

Throughout all phases of our study, subjects will be encouraged to complete the full course of the study assessments. However, it is understood that a subject may discontinue study

participation at any time for any reason. The reason for early withdrawal must be documented in the subject's case file and in the subject tracking document.

Reasons for Withdrawal: Subjects are free to withdraw from the study at any time for any reason. Subjects should normally be withdrawn from the trial if a serious adverse event (SAE) occurs. Subjects **must** be withdrawn from the trial if:

1. They withdraw their consent;
2. The investigator considers it in the best interest of the subject that he or she is withdrawn;

The reason for any subject's discontinuation and the date of withdrawal will be recorded in the subject's case file. The subject's case file, which will be completed up to the point of withdrawal, will be retained for three years. The study report will include reasons for subjects' withdrawals as well as details relevant to the subjects' withdrawals. Any subject withdrawn from the trial prior to completion will undergo all procedures indicated in this protocol as being scheduled to occur at discharge or upon early withdrawal. Any subject withdrawn due to an adverse event (whether serious or non-serious) or any clinically significant abnormal laboratory test value will be evaluated by the Principal Investigator or a monitor (see Key Personnel), and will be treated and followed up until the symptoms or values return to normal or acceptable levels, as judged by the Principal Investigator. Relevant post-study procedures will be performed, wherever possible, on subjects who elect to withdraw.

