Handling of Withdrawal: If a subject is withdrawn from participation in the study at any time at his or her request, at the IRB or Principal Investigator's discretion, the reason(s) for discontinuation shall be documented thoroughly in the source documents and subject's case file. If a subject is discontinued because of an adverse event, this event will be followed until it is resolved or the subject is clinically stable and will also be documented in the source documents and the subject's case file.

8. Study Procedures

Informed consent:

Subjects for each aim will give informed consent to participate in the project. Research Assistants will read, review, and discuss consent forms with all potential participants prior to asking them to sign. If the candidate appears confused or indicates a lack of understanding, the interviewer will attempt to identify the misunderstanding and to explain the form again. Any candidate who still does not comprehend the form will be excluded from the study. We will ask questions to confirm understanding of the material covered in the consent procedure, both open-ended (e.g., "Could you tell me what's going to happen if you enroll in the study?") and closed (e.g. "Will you get free medications from the staff of this research study?" or "what will happen to your medical care after the study?"). Persons who understand the consent form and agree to participate in the study will be asked to sign an authorization for the release of medical information to us. Interviewers will witness and date the signed forms and complete the corresponding. An informed consent checklist will be used to document the participant's understanding of the informed consent process. Consent procedures will take place in a private room or office. Consent forms will be kept in a locked file cabinet within a locked room.

For sub-aim 1.1, we will consent pilot participants once prior to acceptability testing

interview/group discussion and this consent will cover the entire pilot process (acceptability testing, pilot trial procedures, and feasibility testing). For this sub-aim 1.1, we will also be soliciting feedback on the trial design from local HIV Community Advisory Boards (CAB) at UH and Duke as described above. Because there is no identifiable data being collected, we are asking for a waiver of consent for these CAB meetings.

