Visits done between 14 and 28 days after the calculated visit date will be considered a protocol deviation. Visits outside of the +28 day window will not be scheduled and that visit will be considered missing for that patient. The fasting lipid panel blood draw will be done at the time of study visit or within a +/- 10 day window. To limit potential bias, participants, their healthcare providers, and the prevention nurse delivering the education modules will be blinded to the in-office BP outcome measure unless a safety threshold is exceeded (systolic BP <90 or >180mmHg). BP may be re-checked separately as part of routine care.

Control participants will be encouraged to maintain participation in the study in order to minimize differential loss-to-follow-up between intervention and control group that would jeopardize the validity of study findings. As recommended by the design teams, we will conduct semi-annual participant engagement parties (in January and July) that will consist of a meal, healthy lifestyle education and games. We will report enrollment and other study related news to participants. All participants—both intervention and control—will be invited to these events. As an additional incentive, control participants will receive a BP monitor and instructions about its use after completion of the final 12-month trial visit.

EXTRA-CVD intervention: Participants randomized to the intervention will meet with the site prevention nurse on the day of enrollment. With nurse assistance, the participant will complete an initial ASCVD risk assessment using the ACC/AHA risk calculator and a risk visualization tool available at <https://statindecisionaid.mayoclinic.org/>. This exercise will help establish rapport between the participant and the nurse, and will help identify potential targets for intervention. The nurse will conduct a baseline medication assessment, including participant's knowledge of the purpose and side effects of each BP or cholesterol medication and current or potential adherence strategies.

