2. Nurse-managed medication protocols and adherence support. Participants with BP or non-HDL above goal will receive tailored medication management and adherence support. Algorithm-based care to reduce practice variation and clinical inertia has long been recommended to assure that patients are not “stuck” at sub-therapeutic doses of medications⁸². A meta-analysis of nurse and pharmacist-led cholesterol medication adherence interventions showed substantial improvements in adherence and 15-20mg/dL reductions in total cholesterol⁴². By using algorithms and clear decision rules to guide medication titration, the prevention nurse will make recommendations to providers to improve care by reducing clinical inertia, reducing variation, and allowing non-physician staff members to assist in care. A clear and complete algorithm will also help simplify the medical regimen and emphasize medications that are affordable, effective, and have low side-effect profiles.

[figure not shown]
At each visit (in-person or telephone) where recent home BP values (average weekly BP based on a minimum of three values) exceed 130/90mmHg (in line with 2017 ACC/AHA hypertension guidelines), the prevention nurse will review the medication list with the patient, including any recent medication regimen changes and potential side-effects of each medication⁸³. The nurse will provide counseling in several areas, including ways to enhance medication adherence and prevent or ameliorate side effects. For example, patients may be given a personalized medication schedule that shows when they should take their medications.

The prevention nurse will use the algorithms described below to decide on appropriate recommendations for medication changes and will approach the designated responsible provider (HIV, PCP, or non-HIV specialist) for prescriptions and lab orders. *The responsible provider will ultimately decide on final management decisions and may request to have the participant be taken OFF management protocols as clinically indicated (e.g. recent ASCVD events or advanced CKD), in which case the participant would continue all other components of the EXTRA-CVD intervention.*

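### Minor: withdrawal from the trial is the default after any SAE, and no visible text keeps the scheduled outcome BP, so the rule itself creates missing data that MAR methods may not cover

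*Combined protocol and SAP*

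**What the plan says.** Section 7, Reasons for Withdrawal, sets the default: "Subjects should normally be withdrawn from the trial if a serious adverse event (SAE) occurs". It is not limited by cause, severity or arm. A separate list of mandatory reasons holds only withdrawal of consent and the case where "The investigator considers it in the best interest of the subject that he or she is withdrawn".

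After withdrawal, three things are provided for:

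- The case file, "which will be completed up to the point of withdrawal", is retained.
- For a discontinuation due to an adverse event, "this event will be followed until it is resolved or the subject is clinically stable" (Handling of Withdrawal). This is safety follow-up.
- Early-withdrawal procedures are promised, but no visible text lists them. Post-study procedures are mentioned for subjects who choose to leave, also without content.

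Other parts of the protocol lean towards keeping people in. Section 7 opens with "Throughout all phases of our study, subjects will be encouraged to complete the full course of the study assessments". The education control text in Section 8 wants to "minimize differential loss-to-follow-up between intervention and control group that would jeopardize the validity of study findings". Under intervention component 2, a provider may take a participant off the medication protocols, and "the participant would continue all other components of the EXTRA-CVD intervention". Adverse Events Protocols asks for a judgement, event by event, on whether continuing study treatment is safe. Statistical Considerations commits to ITT and to a mixed model valid under MAR, reported with and without multiple imputation.

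**The concern.** An SAE may justify stopping a drug recommendation or the whole intervention. It is seldom a reason to stop measuring the outcome, and under ITT the outcome is still wanted. Here the default removes the participant, and the 12-month BP goes too.

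The loss may be informative. The protocol's Potential risks section names kidney injury, orthostatic hypotension and bradycardia as possible effects of the recommended drugs. Severe cases, like cardiovascular events, can be SAEs tied to BP or its treatment. MAR methods handle loss explained by arm, earlier BP and model covariates. They cannot recover a BP change that comes with or after the SAE and is never measured. The planned comparison with and without imputation does not test for such a change, since neither analysis allows for it.

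In Aim 2 the effect partly cancels between arms. In AAIM-High nothing offsets it in the within-arm change in home BP, which is how Objective 5 would most naturally be read.

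**Working it through.** **Inputs from the documents (Power; Study Design; Aim 4 Enrollment).** SBP SD 17; within-person correlation 0.4; missing 5%, 10% and 15% at 4, 8 and 12 months; 300 randomised 1:1; two-sided 0.05; target 6 mmHg; 110 in AAIM-High.

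**Assumptions.** SAE withdrawal of s = 5% or 10% among those otherwise retained, spread evenly over 12 months. True 12-month BP in those withdrawn differs by d = 5 or 10 mmHg from the MAR prediction. Neither figure is in the documents, and the direction is unknown.

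**1. The plan's own figure.** For the stated model (common intercept, categorical time, arm-by-time terms, random intercept), the information matrix is the sum over arms and dropout patterns of n·p·X′V⁻¹X. The SE is the square root of the 12-month arm element of its inverse. With monotone dropout and n = 150 per arm, SE = 1.941. Power = Φ(6/1.941 − 1.96) = 87.1%, consistent with the stated figure of more than 80%.

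**2. Loss added by the rule.** People who would have dropped out anyway are lost with or without the rule, so the added 12-month loss is 0.85 × s:

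- s = 5%: 0.85 × 0.05 = 4.25 points; total missing 15 + 4.25 = 19.25%.
- s = 10%: 0.85 × 0.10 = 8.5 points; total missing 15 + 8.5 = 23.5%.

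**3. Aim 2 precision (same s in both arms).**

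| s | Missing at 12 months | SE | Power for 6 mmHg |
|---|---|---|---|
| 0 | 15% | 1.941 | 87.1% |
| 5% | 19.25% | 1.988 | 85.5% |
| 10% | 23.5% | 2.039 | 83.7% |

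**4. Aim 2 bias.** Bias = 0.85 × (s_A·d_A − s_B·d_B).

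- Equal s and d in both arms: 0.
- 10% vs 5%, d = 5: (0.085 − 0.0425) × 5 = 0.21 mmHg.
- 10% vs 5%, d = 10: (0.085 − 0.0425) × 10 = 0.43 mmHg.

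With 10% vs 5% the SE is 2.013, so bias/SE is 0.11 to 0.21. Coverage of the 95% interval, Φ(1.96 − b/SE) − Φ(−1.96 − b/SE), is about 94.9% to 94.5%.

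**5. AAIM-High within-arm 12-month change.** The plan states no model for this, so an Aim 2-type mixed model with the office-BP inputs is assumed, n = 110. The SE is 1.874 with no SAE loss, 1.908 at 5% and 1.944 at 10%.

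- Smallest shift: 0.0425 × 5 = 0.21 mmHg, coverage about 94.9%.
- Largest shift: 0.085 × 10 = 0.85 mmHg, 0.85/1.944 = 0.44 SE, coverage about 92.8%.

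**6. AAIM-High against parent-trial participants.** No SE is given here. Aim 4 Enrollment lets each of three sites bring in 5-10 people who completed Aim 2, so 15-30 may be in both groups and an independent-groups SE would not apply.

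**The case against.** The best defence is that the text is softer than it looks. The word 'normally' leaves discretion, SAEs are not on the mandatory list, and Adverse Events Protocols decides case by case on study treatment. That stands, and it rules out reading the rule as compulsory or as contradicting the rest of the protocol. A reader might cite the component 2 provision, which names recent ASCVD events, as a direct conflict. It does not say that those events occur on study, so the documents support tension in wording and no more. Discretion still does not supply a follow-up rule: the default is removal, and the case-by-case text concerns treatment, not outcome measurement.

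Second, some SAE loss may already be in the planned 15%. Power cites 80-88% retention in earlier studies, a loss of 12-20%, and the 19.25% scenario falls inside that range. This also stands and lowers the stakes further. The 5-10% rate has no source in the documents, and the monitoring section expects no real harm to patients.

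Third, the promised early-withdrawal procedures might include a BP. At best that would be a reading at withdrawal, not the scheduled 12-month value. Some pages were removed from the copy reviewed, so the statement covers visible text only.

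Fourth, AAIM-High is a hybrid type 3 study centred on implementation, so a small shift in its BP change matters less than it would in a confirmatory trial. That is fair.

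**Conclusion.** The point holds as a minor one. The rule is explicit, it produces avoidable missing outcomes, and it pulls against the plan's ITT principle and its own concern about differential loss.

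Two stronger inferences are not supported. One is that the rule seriously biases or underpowers Aim 2. Under the assumptions shown, power stays above 83%, bias is zero if the arms match, and it is about a fifth of an SE in the worst case illustrated. The other is that the withdrawal rate can be multiplied directly by the BP departure. That counts people who would have dropped out anyway and overstates the effect by about 18% (1/0.85 = 1.18).

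The largest illustrated effect is 0.85 mmHg, under half an SE, in the AAIM-High within-arm change. It depends on an assumed model, office-BP inputs for a home-BP outcome, and assumed rates and departures. The true size and direction are unknown.

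**What to change.** Replace the SAE sentence with:

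> An SAE does not by itself end follow-up. After an SAE the investigator and responsible provider decide which intervention components stop. Unless the participant withdraws consent to follow-up, or the investigator judges that follow-up itself is not in the participant's best interest, the scheduled 4-, 8- and 12-month outcome BP (in-office in Aim 2; participant-reported home BP in AAIM-High, requested at the scheduled visit even if intervention use of home monitoring has stopped), adverse events and, in Aim 2, lipids are still collected and included in the ITT analysis.

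Reword the best-interest rule so that it applies first to the intervention and ends follow-up only when follow-up itself is harmful. Otherwise the two rules would give opposite instructions.

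For participants already withdrawn after an SAE, report counts by arm. This extends what the protocol already promises ("The study report will include reasons for" withdrawal). In Aim 2, add one sensitivity analysis that shifts their imputed 12-month SBP by ±5 and ±10 mmHg.

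The cost is an IRB amendment, a few follow-up contacts within the existing schedule and one extra analysis. Timing limits the gain. The version is dated September 23, 2022, the Aim 4 Timeline expected the last AAIM-High visits in June 2022, and Appendix S refers to a 30-month trial period. The October 2021 rise in the enrolment goal to 110 probably moved the AAIM-High end date later, but actual dates are not given. If follow-up was nearly complete, mainly the reporting and the sensitivity analysis remain useful.
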